## **12. DATA AND SPECIMEN BANKING\* N/A**

### **13. Data Analysis and Management\***

All data will be double entered and linked by a common identification number across data sources. We will minimize missing data through careful checking of all surveys and data forms at the time of completion. Baseline characteristics of participants who drop out will be compared to those who complete the study.

Analyses for Specific Aim #1. The process measures of feasibility will assess attendance, degree of participant enjoyment, and participant and parental satisfaction based the aforementioned surveys. These measures will be summarized as means and proportions, with corresponding 95% confidence intervals, and compared across the two waves. If there are no important differences, we will pool across waves. We will use the 6-week and 12-week measures to assess if engagement builds, sustains or declines over the intervention period. We will also examine study completion and attendance by wave.

Analyses for Specific Aim #2a. To assess if the intervention increases aspects of physical literacy including movement competence (ability), confidence, and desire to participate in physical activity, we will conduct 1-sample paired t-tests for change (against the null hypothesis of a change of zero) in separate tests for TGMD-3 scores, PSI-VSF-ID physical self-concept, and CSAPPA score. We will construct 95% confidence intervals around the measure of change separately for boys and girls, and pool them if we discern no important differences by sex. If, based on Aim #1, we believe there were important implementation differences between the two waves, we will analyze them separately, acknowledging our power will be more limited.

Analyses for Specific Aim #2b. Analyses to assess if the intervention increases elements of food literacy (i.e., knowledge and skills) for promoting intake of fruits and vegetables and for decreasing intake of high energy low nutrient dense snack foods will proceed as for Aim #2a. We will use a 1-sample (paired) t-test to test Food Knowledge, Food Skill Master, and Dietary Behavior scores. We will construct 95% confidence intervals around the change separately for boys and girls, pooling them if we discern no important difference by sex. If, based on Aim #1, we believe that there were important implementation differences across the two waves, we will analyze them separately, acknowledging our power will be more limited.

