Sample Size Considerations. We established the sample size for this pilot study based on the aforementioned total and skill score on the CAMSA (Specific Aim #2a). Using available estimates from TD adolescents, we calculated the sample sizes needed to capture a 15% change

in score for boys and girls separately (score improvements of 6.63 total; 3.66 skill). Estimates on the CAMSA from adolescents with ID are unavailable in the literature; however, we have no reason to believe that the proposed intervention would have a different impact on adolescents with ID than TD adolescents. We estimated the standard deviation of the change in the measure (5.19 total; 3.10 skill) and the interclass correlation coefficient (0.91 total; 0.80 skill), as recommended. A sample size of 12 boys and 12 girls has, at an alpha level of 0.05, 80% power to assess a difference of 15% in total score and 15% in skill score, analyzing boys and girls separately. We have proposed to enroll 15 boys and 15 girls in our pilot study to allow for attrition and or missing data. If we do not identify important differences in the change in score by sex we will combine them, with the result that we would have adequate power to detect changes of the magnitude ~5% total and skill scores.

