## **24. LOCAL RECRUITMENT METHODS**

### **Recruitment.**

Participants with ID will be recruited through area special education programs and schools, as well as through the many agencies that serve individuals with ID and their families such as local Arc chapters, city/town recreation programs, Federation for Children with Special Needs, MA Down Syndrome Congress, Department of Developmental Services, and MA Special Education Parent Advisory Councils. We will use our extensive connections in the community and the UMass Chan E.K. Shriver Center's database of participants from previous studies to reach adolescents with ID. We aim to recruit a racially/ethnically diverse sample via postings to listservs, websites, phone, paper mailings, newsletters, and word of mouth. IRB-approved recruitment will be conducted locally using materials that are mailed or distributed via social media to organizations that serve youth with ID. We will continue to submit all recruitment materials via a modification prior to utilizing the recruitment material.

Recruitment materials (e.g. e-brochures, electronic messages) will clearly outline the details of the study and a parent/guardian will directly contact the research staff by telephone or email to express their interest in having their child participating. The intervention will be marketed as a non-competitive and engaging program involving sport skills sampling and healthy eating awareness activities to build physical literacy and food literacy.

Our research plan allows for a 10% drop out rate, which is supported by our previous work in which we have had over 95% retention rates in several intervention studies.

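### The two power claims in the sample-size paragraph fit neither each other nor the printed SDs: as labelled, pooled power for a ~5% change is 46–62%

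*Combined protocol and SAP*

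**What the plan says.** All the power reasoning is in section 13, Sample Size Considerations, and concerns the CAMSA total and skill scores.

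- Target: "we calculated the sample sizes needed to capture a 15% change", done for each sex separately, with "score improvements of 6.63 total; 3.66 skill".
- Variability: "We estimated the standard deviation of the change in the measure (5.19 total; 3.10 skill"), together with "the interclass correlation coefficient (0.91 total; 0.80 skill), as recommended".
- Per-sex statement: "A sample size of 12 boys and 12 girls has, at an alpha level of 0.05, 80% power to assess a difference of 15" per cent, each sex analysed on its own.
- Pooled statement, for the sexes combined: "we would have adequate power to detect changes of the magnitude ~5% total and skill scores". No power figure is attached.

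Fifteen of each sex are to be enrolled. Section 24 (Recruitment) adds: "Our research plan allows for a 10% drop out rate". The planned analysis for Aim 2a, also in section 13, is "1-sample paired t-tests for change (against the null hypothesis of a change of zero) in separate tests for TGMD-3 scores" and other scales. The sidedness of the 0.05 level is not stated.

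**The concern.** Detectable change shrinks roughly with the square root of the sample size. Going from 12 to 24 or 30 participants should improve it by a factor of about 1.4 to 1.6, but the plan moves from 15% to about 5%, a factor of three. That would need roughly nine times the participants (12 × 9 = 108). The stated SDs, used as labelled in the planned test, also do not appear to give 80% for the per-sex statement.

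This is the only power statement in the plan. A reader who trusts the ~5% figure could take a non-significant pooled result as evidence against small effects that the study was unlikely to detect.

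**Working it through.** **Inputs** (total / skill; section 13 unless noted)

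- 15% change: 6.63 / 3.66. Implied baselines are 6.63/0.15 = 44.2 and 3.66/0.15 = 24.4, so 5% is 2.21 / 1.22.
- SD labelled as that of the change: 5.19 / 3.10. ICC: 0.91 / 0.80.
- n: 12 per sex; pooled 24, or 30 as enrolled, or 30 × 0.9 = 27 with the 10% dropout of section 24.
- Test: paired t against zero change, alpha 0.05. Two-sided is assumed; one-sided is shown as well.

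**Formula.** Power = P(|T| > t(0.975, n−1)), where T is noncentral t with n−1 degrees of freedom and noncentrality (change/SD) × √n.

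**1. The plan's own figure: 15% with n = 12.** Standardised change is 6.63/5.19 = 1.277 and 3.66/3.10 = 1.181. Power is 98.0% / 96.0% (one-sided 99.4% / 98.5%). For 80%, 7 / 8 per sex would do. The stated 80% is not reproduced.

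Two other routes come nearer, but neither is the planned test with the SDs as labelled:
- A two-independent-sample normal formula gives 10 / 12 per group, with power 87.9% / 82.4% at 12.
- A paired t-test with SD × √2 (7.34 / 4.38) gives 81% / 75%.

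**2. Pooled, 5% change, SDs as labelled.** Standardised change is 2.21/5.19 = 0.426 and 1.22/3.10 = 0.394.

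| n | Power, two-sided | Power, one-sided | Detectable at 80% power, two-sided |
|---|---|---|---|
| 24 | 51.5% / 45.5% | 64.8% / 58.9% | 7.0% / 7.6% |
| 27 | 56.8% / 50.4% | 69.5% / 63.5% | 6.6% / 7.1% |
| 30 | 61.6% / 54.9% | 73.6% / 67.7% | 6.2% / 6.7% |

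Two-sided 80% power for 5% needs 46 / 53 participants.

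**3. A check that does not depend on the SD.** The standardised change detectable with 80% power (two-sided) is 0.889 at n = 12, 0.597 at 24, 0.560 at 27 and 0.529 at 30. Suppose n = 12 gives exactly 80% for 15%:

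- Pooled detectable change: 15% × 0.597/0.889 = 10.1% at n = 24, and by the same ratio 9.45% at 27 and 8.9% at 30.
- Power for 5%: 28.5%, 31.7% and 34.8%. Reaching 80% would need 92 participants.
- One-sided: 10.2% detectable at n = 24, and 33–39% power for 5% over the three sizes.

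An 80% reading of the per-sex statement implies SDs of change of 6.63/0.889 = 7.46 and 3.66/0.889 = 4.12. For the pooled statement (n = 24) it implies 2.21/0.597 = 3.70 and 1.22/0.597 = 2.04. The printed 5.19 / 3.10 lie between, so the claims miss in opposite directions.

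**4. SDs read as single-occasion values.** SD of change = SD × √(2(1 − ICC)): 5.19 × √0.18 = 2.20 and 3.10 × √0.40 = 1.96. Pooled power for 5% at n = 24 is then 99.7% / 83.1%. Power for 15% at n = 12 exceeds 99.9%, and 4 / 5 per sex would give 80%.

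**The case against.** The strongest reply is that 46–62% rests on the reading that fits the paragraph least well. If 5.19 and 3.10 really are SDs of change, neither claim comes out and the ICCs have no role in a paired t-test. If they are single-occasion SDs, the ICC conversion supports ~5%, and SD × √2 comes close to 80% for 15% at n = 12. That pattern suggests a mislabelled SD rather than an overstated pooled claim. In addition, the pooled claim carries no power figure, 12 need not be the minimum n, and the derivation may be in the grant application, which is not part of these documents.

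Much of this stands: the SD label may be the faulty item, and 46–62% must stay conditional on it. It does not rescue the paragraph. The ICC-converted reading makes both claims literally true only if 80% is a loose floor under more than 99.9%, which sits badly with sample sizes described as needed. The √2 reading leaves 26–36% pooled power for 5%. Neither agrees with the printed label, and 80% is the only benchmark the paragraph offers.

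It is also fair that n = 24 means 20% loss. With the planned 10% loss (n = 27), power as labelled is 50–57%.

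**Conclusion.** The concern holds. The printed inputs do not give the printed power, and at least one of the SD label, the 80% figure and the ~5% figure needs correcting. The documents do not show which.

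- The conflict between the two claims assumes that 80% is the design power; it needs no assumption about the SD.
- The 46–62% assumes the SD label is right, a two-sided test and n = 24 to 30. One-sided it is 59–74%, still below 80%.

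The consequence is limited. Feasibility is the first aim, 95% confidence intervals are already planned, and 12 per sex exceeds 80% for a 15% change both as labelled and on the ICC-converted reading. The CAMSA is not among the outcome measures in section 10, so these percentages cannot be applied directly to the TGMD-3 that will be tested. The point should be fixed, but it does not call the study design into question.

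**What to change.** Go back to the original calculation and state in section 13 the formula, the sidedness, whether 5.19 and 3.10 are SDs of change or single-occasion SDs, and how the ICC enters. Then restate both figures:

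- **If the label is right (two-sided):** report 96–98% power for 15% with 12 per sex, and replace ~5% with the detectable changes tabulated above for n = 24, 27 or 30.
- **If the SDs are single-occasion and ICC-converted:** relabel them, keep ~5%, and correct the 80%.
- **If ~5% was meant as precision:** say so. As labelled, the 95% CI half-width at n = 24 is 2.19 / 1.31 points, or 5.0% / 5.4% of baseline. This origin is only a possibility for the authors to check.

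Because the TGMD-3 is the measure tested, also give the detectable standardised change (80% power, two-sided): 0.89 SD of change at n = 12, 0.60 at 24, 0.56 at 27 and 0.53 at 30.

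The cost is one reworded paragraph and no extra participants. If the label is right, the stated pooled sensitivity becomes less favourable.

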#### **14. PROVISIONS TO MONITOR THE DATA TO ENSURE THE SAFETY OF SUBJECTS\***

The physical and food literacy intervention and measurement protocols pose minimal risks to participants. As a supervised sport sampling and healthy eating program that requires approval from each participant's primary care physician and medical specialists (as needed), the proposed study represents a low-risk intervention. The intensity of the sports/physical activities will be guided and monitored by a physical activity instructor with experience instructing adolescents with ID and an academic background in exercise science and/or physical education. The healthy eating activities will be delivered by an experienced nutritionist/registered dietitian with at least an undergraduate degree in nutrition. Because of the minimal risk, the data safety monitoring plan for this study focuses on close monitoring by the PI and a data safety officer, along with prompt reporting of excessive and/or unexpected serious adverse events to the NIH and to the IRB at UMass Chan.

We have identified a data safety officer for this study who has experience conducting physical activity/health promotion intervention studies for adolescents and youth with neurodevelopmental and behavioral health disorders, and thus has a thorough understanding of the issues that arise in a combined program of this type. The data safety officer will review reports of any adverse events or unanticipated problems recorded by the study team. Although highly unexpected, participants could be injured during their physical activity participation or choke on food during the taste tests. We have not experienced these types of events in our previous studies and programs, but they are within the realm of possibility. We will mitigate these risks by providing close supervision of the participants so they do not engage in risky physical behaviors (e.g., over-exertion) or engage in problematic eating behaviors (e.g., over-stuffing their mouths or rapid eating).

The data safety officer will use a checklist to indicate whether there is any corrective action, trigger of an ad hoc review, or stopping rule that should be communicated to the study investigators, the UMass Chan IRB, or the NIH institute to which the project has been assigned. In addition, the data safety officer will comment on whether the PI needs to report any specific concerns to the participant, their parent(s), and/or their primary care physician.

**Personal identifying information (PII).** The names of the participants will be obtained to ensure that the data are organized during data collection and for the intervention. Names will be transferred to a participant number when the data are entered into the computer and no names

will ever be published. Age and birthdate will also be required as will sex. The addresses and telephone numbers of the parent(s) of each participant will be required in order to maintain contact during the intervention. There will be no attempt to link the PII to the study data.

## **15. WITHDRAWAL OF SUBJECTS WITHOUT THEIR CONSENT\***

Although we do not anticipate the need to withdraw participants without their consent, if we find that an individual adolescent is unable to participate in the program safely (i.e., to keep him/herself or others safe), we will first seek to address the behavior (i.e., address anxiety or other issues that might be leading to the problematic behavior), and engage the adolescents' parents in problem-solving. If those efforts are not successful, we will proceed to withdraw the adolescent from the study.

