### **(2) Feasibility Measures**

Process measures of demand, acceptability, and implementation will be obtained as follows:

- *Demand* will be assessed by documenting number of inquiries into the program and number of participants screened and enrolled. Attendance will be recorded for each session and we will document reasons for any absences. Withdrawal, date of withdrawal, and reasons will also be documented.
- *Acceptability* will be assessed via participant and parent surveys of enjoyment, satisfaction, and perceived appropriateness at weeks 6 and 12. Surveys will be adapted from those used in our previous work, and will include close-ended questions with Likert scale response options and opportunities for open-ended feedback. The participant survey will be simple and will include visual cues (e.g., happy face for “like it”) to assist in understanding questions and response choices. The survey will be administered orally and will take about 15 minutes. Participants will be queried about program elements such as: appropriateness and enjoyment of the sport/healthy eating activities; sports equipment; support/instructional methods used by staff; using Zoom to conduct the intervention remotely; barriers/facilitators of participation in physical activity and healthy eating; enjoyment of interactions with other adolescents; preferred sports and taste test foods; perceived improvements in physical/food literacy; and enjoyment/perceptions of “*Bring it Home and Give it a Try*” activities. Parent satisfaction via a survey will query perceptions such as: program quality; benefits to adolescent; staff effectiveness; appropriateness of activities; adolescent enjoyment; quality of the facility; and barriers to/facilitators of participation.
- *Implementation* will be assessed via documenting the factors affecting program implementation and sufficiency of resources (e.g., space, staff), and fidelity checks. Through observation and discussions with staff, participants, and parents, we will document: adaptations made to increase success; effective/ineffective strategies used to promote participation; most appropriate sports; quality of activity sessions; and barriers and facilitators encountered. Fidelity checks will be conducted in 25% of the program

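### No post-intervention measures are provided for adolescents who leave the study, so the Aim 2 paired tests use only those with both scores, and the mean change is overstated if leavers gain less

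*Combined protocol and SAP*

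**What the plan says.** Section 15 deals with withdrawal without consent. It applies "if we find that an individual adolescent is unable to participate in the program safely". The team first tries to resolve the behaviour and brings in the parents; if that fails, "we will proceed to withdraw the adolescent from the study". The condition concerns the program and the consequence concerns the study. The section does not say whether outcome measurement continues.

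Section 10 schedules the physical and food literacy measures at baseline and after the 12 weeks, and describes no assessment after withdrawal. Under Feasibility Measures, attendance and reasons for absence are recorded session by session, and "Withdrawal, date of withdrawal, and reasons will also be documented".

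On missing data, Section 13 says: "We will minimize missing data through careful checking of all surveys and data forms at the time of completion". On dropouts it says: "Baseline characteristics of participants who drop out will be compared to those who complete the study". Aim 2a tests change against zero with paired t-tests. For Aim 2b, "We will use a 1-sample (paired) t-test to test Food Knowledge, Food Skill Master, and Dietary Behavior scores". Section 13 defines no analysis set for these tests and gives no method for a missing post score.

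Several outcomes do not depend on the group sessions. Section 10 has parents answer the YRBSS diet questions and the FFQ, and has the self-concept and CAPL-2 questionnaires and the food-knowledge test given over Zoom. Section 11 places the baseline round of these measures at enrollment, before any session, and lets parents fill in their own forms offline. Section 16 sees no discernible risk in the questionnaire measures and puts the TGMD-3's risk no higher than that of the sessions.

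**The concern.** This is a single-group study that tests change against zero, so no control arm would share the loss. An adolescent who is withdrawn has no planned post score and drops out of every paired test. The estimate then describes those who stayed and were measured, not those who enrolled.

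An adolescent who stops early has received less of the program, so a smaller gain is plausible, and in that case the reported mean change is too large. Section 4 makes a larger controlled study the next step if this one succeeds, so the estimate is likely to be used.

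Part of the loss is avoidable. The Section 15 trigger is safety in the program, and on Section 16's own account that reason does not extend to a parent questionnaire or a questionnaire given over Zoom.

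**Working it through.** **Inputs from the documents**
- Enrolled: 30, as 15 boys and 15 girls (Section 6).
- Dropout allowance: 10%, with retention above 95% reported in several earlier studies (Section 24). Section 4 also hypothesises dropout of at most 10%.
- Sizing: 12 per sex needed and 15 enrolled, the margin being for attrition or missing data (Section 13).

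**The plan's own figures.** The plan gives no figure for this bias. Its dropout allowance is 0.10 × 30 = 3 adolescents. Its enrolment margin is reproduced by 12 / (1 − 0.20) = 15 per sex, or 6 of 30.

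**Assumption.** Let those measured at both times have mean change g, and the m who leave have mean change k × g. The documents give no value of k, so a range is shown.

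**Formula.** The mean for all enrolled is g × [(30 − m) + m × k] / 30. The relative overstatement is therefore 30 / [(30 − m) + m × k] − 1.

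**One withdrawal (m = 1)**
- k = 0: 30/29 − 1 = 3.4%
- k = 0.5: 30/29.5 − 1 = 1.7%

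**The plan's 10% dropout (m = 3)**
- k = 0: 30/27 − 1 = 11.1%
- k = 0.5: 30/28.5 − 1 = 5.3%
- k = 1: 30/30 − 1 = 0%
- k = 1.5: 30/31.5 − 1 = −4.8%, an understatement
- k = −0.5 (leavers worsen): 30/25.5 − 1 = 17.6%

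**Loss of 5%, in line with past retention**
- k = 0: 1/0.95 − 1 = 5.3%
- k = 0.5: 1/0.975 − 1 = 2.6%

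**Smaller groups.** Section 13 also plans estimates by sex, and by wave if implementation differs. One zero-gain loss gives 15/14 − 1 = 7.1% in a sex group, and 10/9 − 1 = 11.1% in a wave of 10 (Section 9).

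**Scale against sampling error.** Section 13's planning values are for the CAMSA, which is not among the Section 10 measures, so this is illustration only. With a completer gain of 6.63 total points, m = 3 and k = 0, the bias is 6.63 × 0.10 = 0.66 points. The 95% confidence half-width at n = 27 with an SD of change of 5.19 is 2.056 × 5.19 / √27 = 2.05 points.

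**The planned safeguard.** Comparing about 3 dropouts with 27 completers at baseline may show a difference. It cannot show that loss is unrelated to change, and it does not alter the estimate.

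**The case against.** Section 15 is the rarest route to loss. It covers involuntary withdrawal only, after other efforts fail. It states that "we do not anticipate the need to withdraw participants without their consent", and Section 6 excludes habitual problem behaviour at entry. This stands: Section 15 alone is worth about 3.4% per zero-gain case. The gap in post-withdrawal measurement, however, applies to leaving for any reason, and the plan budgets for that at 10%.

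Three stronger readings are tempting, and the documents do not support them.
- **That missing sessions means leaving the study, or that the tests are limited to those who finished the program.** Section 10 records attendance separately from withdrawal, and Section 13 sets no attendance threshold. The restriction to adolescents with both scores is an inference from a paired test with no later assessment; it is not a stated analysis set.
- **That the gain will be overstated.** This needs leavers to gain less, and no figure in the documents shows it.
- **That the bias could reach 25%.** That is 30/24 − 1, which treats the whole enrolment margin as zero-gain dropout. The margin also covers missing data, and the dropout allowance is 10%.

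The bias is also small beside the sampling error of a pilot, as the illustration shows. That limits its importance but does not remove it, since a larger sample would not shrink it. The consent pages and grant narrative were not available for this review and might address measurement after withdrawal. If they do, Sections 13 and 15 should say the same.

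**Conclusion.** The point holds as a modest, avoidable risk of bias. Followed as written, the protocol obtains no post score from an adolescent who is withdrawn, the paired tests omit that adolescent, and the baseline comparison does not repair this. At the plan's 10% dropout, the overstatement is about 5% to 11% if leavers gain between half as much and nothing. It is zero if gains are equal, and becomes an understatement of about 5% if leavers gain half as much again. These figures rest on an assumed k and on no post scores being obtained from leavers. The issue does not undermine the feasibility aim. It is worth correcting because the remedy costs little and the estimate is meant to inform a controlled study.

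**What to change.** **Section 15.** Separate stopping the sessions from leaving the study. The decision about when an adolescent stops the sessions stays as it is.

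**Sections 10 and 15.** State that anyone who stops the sessions, for whatever reason, is still invited at the scheduled time, with parent permission and adolescent assent, to the post-intervention measures. These are the parent-reported YRBSS questions and FFQ, the Zoom questionnaires and the food-knowledge test. Whether to offer the TGMD-3 is left to the team's judgement.

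**Section 13.** State that the Aim 2 analysis includes everyone with both measures regardless of attendance. Add a sensitivity analysis for scores still missing, over a range of assumed changes, for example zero and half the mean change of those with both scores. Report it as a shift in the estimate, because filling in a constant understates uncertainty.

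**Cost.** Protocol wording and a few extra questionnaire contacts by existing staff, about three families at the planned dropout. Some families will decline. The estimated change may be smaller and more variable.
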